The derived variables containing the ^[a] flag in [Table 9-1](#) above will be listed together with information on staining artifacts and any assay-specific comments provided by the laboratory.

Observed values for total relative FAP-positive tumor area (TPS) and total FAP histoscore will be summarized using descriptive statistics (n, arithmetic mean, standard deviation, median, minimum and maximum) at each timepoint (Historical, Baseline and On-Treatment) by treatment group. In addition, changes from Baseline in TPS and total FAP histoscore at the On-Treatment timepoint will be listed and summarized by treatment group.

pSMAD1/5/8: Nuclear Histoscore

All pSMAD1/5/8 raw test results will be listed.

The nuclear histoscore will be calculated as a weighted score based on the percentage of tumor cells with pSMAD1/5/8 nuclear staining intensity 1+, 2+ or 3+ as follows:

$$(1 \times \text{percent tumor cells with pSMAD1/5/8 nuclear staining intensity 1+}) + (2 \times \text{percent tumor cells with pSMAD1/5/8 nuclear staining intensity 2+}) + (3 \times \text{percent tumor cells with pSMAD1/5/8 nuclear staining intensity 3+}).$$

The histoscore will be missing if the participant had tumor biopsy samples analyzed but there are no test results for percent tumor cells with pSMAD1/5/8 nuclear staining intensity 1+, 2+ or 3+.

Summary statistics (n, arithmetic mean, standard deviation, median, minimum and maximum) will be presented at each timepoint (Historical, Baseline and On-Treatment) by treatment group the nuclear histoscore and the tumor proportion score.

Further informal analyses may be performed to explore the relationship between the PD and biomarker endpoints with antitumor activity and ADA status. The PK-PD effects of UCB6114 may be assessed using a population analysis approach. These analyses will also be performed separately outside of the CSR and the details of analysis methods will be included in a separate analysis plan.

The incidence of PD samples taken from the blood and tumor biopsies will be summarized by visit/timepoint and treatment group.

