3 DATA ANALYSIS CONSIDERATIONS

3.1 General presentation of summaries and analyses

All TFLs will be produced by ICON PLC using SAS® Version 9.4 or higher (SAS Institute, Cary, North Carolina, USA). ICON PLC will also produce the analysis datasets which will adhere to the Clinical Data Interchange Standards Consortium (CDISC) guidance documents for Analysis Data Model (ADaM) and follow UCB's interpretation. General statistical and reporting conventions will follow the current UCB Global Conventions Document Version 1.1.

Data will be summarized by UCB6114 dose schedule cohort (treatment group), visit and timepoint, as applicable. All relevant reported and derived data will be listed and will be presented by treatment group, study participant and visit, as applicable.

Categorical variables will be summarized using frequency counts and percentages. Unless otherwise stated, the denominator for the percentages will be based on the number of participants in the respective analysis set, treatment group, visit and timepoint (as applicable) with non-missing data.

When reporting frequency counts and percentages, the following rules apply:

- For categories where all participants fulfill certain criteria, the percentage value will be displayed as 100;
- For categories where zero participants fulfill certain criteria, there will be no percentage displayed;
- All other percentage displays will use 1 decimal place.

Summary statistics will be presented for continuous variables including number of participants (n), arithmetic mean, standard deviation, median, minimum and maximum. 95% confidence intervals (CIs) for the arithmetic mean may also be included depending on the variable and where stated in the SAP. Geometric mean (geoMean), geometric coefficient of variation (geoCV) and 95% CI for the geoMean will also be presented in the summaries of UCB6114 concentration data. In all relevant outputs the 95% confidence limits will be restricted to the possible values that the variable can take.

When reporting descriptive statistics for data other than UCB6114 concentration data, the following rules will apply:

- n will be an integer;

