- Mean (arithmetic and geometric), standard deviation, median and quartiles will use 1 decimal place more, or 1 significant figure more – depending on the reporting format of the original data – than the original data. Original data may be data as reported directly onto the eCRF or summary data based on data reported onto the eCRF (e.g. mean of triplicates or percentage change from Baseline);
- Confidence intervals will be presented to the same number of decimal places as the value around which the CI is constructed;
- Minimum and maximum will be reported using the same number of decimal places or significant figures as the original value;

- A minimum of 3 values are required to calculate summary statistics. If only 2 values are available, then these should be presented as the minimum and maximum with other summary statistics reported as missing (“- “); if no participants have data at a given timepoint, then only n=0 will be presented;
- Percentage change from Baseline values will be calculated and displayed to 1 decimal place in the listings. In the summaries, where applicable, the mean, standard deviation and median percentage change from Baseline values will be presented to 2 decimal places and the minimum and maximum values presented to 1 decimal place.

[figure not shown]
When reporting individual UCB6114 concentration data in listings and figures, and presenting summary statistics in tables, the following rules will apply:

- UCB6114 concentration data should be reported in the listings to the same level of precision as received from the bioanalytical laboratory;
- Missing data should be reported as ‘NV’ (no value) in the listings;
- Concentrations below the lower limit of quantification (LLOQ) should be reported as BLQ (below the limit of quantification) in the listings;
- BLQ values prior to C_{max} should be set to 0 for purposes of plotting a figure (to capture lag-time);
- Actual sampling times will be used in the spaghetti plots of individual PK concentrations over time, and nominal sampling times will be used in the summaries of geoMean concentrations over time;
- UCB6114 concentration data should be plotted on both linear and semi-logarithmic scales;
- To calculate summary statistics, BLQ values should be set to half the LLOQ value and missing values should be excluded;

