3.3 Definition of Baseline values

Baseline in Part A1 will be the last available value prior to the first dose of UCB6114. Both scheduled and unscheduled values, as well as any repeated values, should be used when defining Baseline.

Measurement-specific Baseline definitions are presented in [Table 3-1](#) below.

Table 3-1: Definition of Baseline

Measurement	Definition of Baseline
Echocardiogram (LVEF) Tumor assessments (antitumor activity) Tumor biopsy (Ki67, SMAD4, FAP, pSMAD1/5/8)	Screening value
12-lead ECG Physical examination and weight Vital signs Clinical laboratory data ECOG performance status	Predose value obtained on Cycle 1, Day 1, or, if missing, Screening value
Circulating gremlin-1 (cGremlin-1) Immunogenicity (ADA)	Predose sample value obtained on Cycle 1, Day 1

ADA=anti-drug (UCB6114) antibody; ECG=electrocardiogram; ECOG=Eastern Cooperative Oncology Group; LVEF=left ventricular ejection fraction.

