9.1.2 Exploratory pharmacokinetic endpoints

9.2 Pharmacodynamics

The following exploratory PD and biomarker endpoints/analyses will be obtained/Performed from blood samples which will be analyzed at a number of external laboratory vendors:

- cGremlin-1;
- Serum protein/proteomic analysis;
- Transcriptomic analysis;
- Genetic analysis;
- ctDNA.

For all cohorts, blood samples for cGremlin-1 analysis will be collected on Day 1 of Cycle 1 at the following timepoints relative to the UCB6114 infusion: predose (within 30 minutes prior to the infusion), end of the infusion (+15 minutes) and 4 hours (+1 hour) postinfusion. For Cohorts 1, 2 and 4, a blood sample will be collected predose (within 30 minutes prior to the infusion) on Day 15 or on the day of the Day 15 visit if this is not a dosing day (Cohort 4). For Cohort 3, a blood sample will be taken on Day 15. In all subsequent cycles for all cohorts, blood samples will be collected at predose (within 30 minutes prior to the infusion) on Day 1 and at the SFU visit. For Cycle 3 only, an additional sample will be taken on Day 1. An additional sample should also be collected on the day of the On-Treatment biopsy (only if taking place on a day where no samples for cGremlin-1 are scheduled).

cGremlin-1 will be reported as concentration in blood by nominal (scheduled) assessment and treatment group. Concentrations of cGremlin-1 will be listed for the SS and summarized for the PDS using descriptive statistics by treatment group and nominal (scheduled) sampling timepoints (n, arithmetic mean, median, standard deviation, minimum, maximum, geoMean, geoCV and 95% CI for the geoMean [assuming lognormally distributed data]). Changes from Baseline will also be summarized. Individual study participant cGremlin-1 concentration-time profiles will be displayed graphically in spaghetti plots and geoMean cGremlin-1 concentration and 95% CI will be plotted at each nominal (scheduled) timepoint with treatment group overlaid on the same plot.

Serum protein/proteomic analysis, transcriptomic analysis, genetic analysis and the analysis of the test results from the blood samples taken for ctDNA will be performed and reported separately outside of the CSR.

Hematoxylin and eosin (H & E) staining and immunohistochemistry (IHC) will be used to analyze tissue samples obtained from any available historical tumor biopsies taken prior to participants' entry into the study (e.g. at the time of diagnosis), from the tumor biopsy performed

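### cGremlin-1 is summarized as lognormal, but its change from Baseline has no relative scale and no paired ratio with a CI is planned (minor)

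*SAP*

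**What the plan says.** The wording is the same in the Part A and Part A1 SAPs on each item below.

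- **Concentration (section 9.2).** cGremlin-1 is summarized by treatment group and nominal timepoint with arithmetic statistics plus "geoMean, geoCV and 95% CI for the geoMean [assuming lognormally distributed data". The figure follows suit: "geoMean cGremlin-1 concentration and 95% CI will be plotted at each nominal (scheduled) timepoint".
- **Effect (section 9.2).** The only provision is "Changes from Baseline will also be summarized". No scale and no list of statistics is given.
- **Default statistics (section 3.1).** "Summary statistics will be presented for continuous variables including number of participants (n), arithmetic mean, standard deviation, median, minimum and maximum". Geometric statistics are added for drug concentration only: "95% CI for the geoMean will also be presented in the summaries of UCB6114 concentration data".
- **Relative change (section 3.1).** Percentage change is a separately named quantity with its own display rule: "Percentage change from Baseline values will be calculated and displayed to 1 decimal place in the listings". In the summaries it appears where applicable. Section 9.2 does not call for it for cGremlin-1.
- **Baseline (section 3.3).** "Predose sample value obtained on Cycle 1, Day 1".
- **Predose rule (Part A section 4.2.1; Part A1 section 4.3).** Under a heading that covers both pharmacokinetics and pharmacodynamics, the value before the first dose is taken as zero. BLQ handling is referred back to section 3.1, where BLQ values become half the LLOQ for summary statistics.

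**The concern.** The concentration is described on a multiplicative scale and the effect, by default, on an additive one. If the drug multiplies cGremlin-1 by roughly the same factor in everyone, a participant's difference is that factor minus one, times the Baseline. The mean difference in a cohort then reflects who was enrolled as well as what the drug did. Cohorts are small (3 to 6 evaluable participants in Part A, up to 8 in Part A1) and not randomized. A chance difference in Baseline levels could therefore be read as a dose or schedule effect on the circulating form of the target. The quantity that fits the SAP's own distributional assumption, the within-participant ratio with its CI, appears in no planned output.

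**Working it through.** The SAP states no figure on this point, so there is none to reproduce. It also gives no spread for cGremlin-1. **Assumed:** Baseline geoCV of 50% to 100%, and a common fold change in all participants.

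**1. Log-scale SD.** Section 3.1 defines geoCV = sqrt(exp(SD²) − 1), so SD = sqrt(ln(1 + geoCV²)).
- geoCV 50%: sqrt(ln 1.25) = 0.472
- geoCV 100%: sqrt(ln 2) = 0.833

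**2. Weight of the highest Baseline.** With fold change r, participant i changes by (r − 1)·Bᵢ. That participant's share of the total is Bᵢ/ΣB, whatever r is. Mean share of the largest value in simulated lognormal cohorts:

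| n | Equal weight | geoCV 50% | geoCV 100% |
|---|---|---|---|
| 3 | 33.3% | 47% | 56% |
| 6 | 16.7% | 28% | 38% |
| 8 | 12.5% | 23% | 32% |

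At n=8 the share is about 18% for a geoCV of 30% and 38% for 150%.

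**3. Effect on comparisons.** Take two cohorts of 8 with an identical fold change. The larger mean change divided by the smaller has a median of 1.18 (geoCV 50%) to 1.37 (geoCV 100%). It exceeds about 1.5 to 2.2 in one pair of cohorts in ten. The geometric mean ratio would be the same in both cohorts.

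**4. Can the planned geometric means stand in?** With complete pairs, yes for the point estimate: mean(ln Y) − mean(ln B) = mean(ln(Y/B)), so the ratio of the two geometric means equals the geometric mean of the ratios.

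If only k of 8 participants have a post-dose value and the rest are missing at random, the unpaired ratio differs from the paired one by exp(mean ln B over the k − mean ln B over all 8). The log of this has variance SD²·(1/k − 1/8). The 5th to 95th percentile factors are exp(±1.645·SD·sqrt(1/k − 1/8)):

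| Missing | geoCV 50% | geoCV 100% |
|---|---|---|
| 2 of 8 | 0.85–1.17 | 0.76–1.32 |
| 3 of 8 | 0.81–1.24 | 0.69–1.46 |

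Section 3.1 drops all statistics except minimum and maximum when BLQ and missing values exceed one third. If that rule carries over to cGremlin-1 and participants who have left count as missing, then at 3 of 8 (37.5%) no geometric mean would be shown at all.

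**5. The CI.** The variance of ln(Y/B) is Var(ln Y) + Var(ln B) − 2·Cov(ln Y, ln B). The two separate CIs do not supply the covariance, so a CI for the ratio cannot be recovered from them even with complete pairs.

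**6. An adverse example.** Seven participants with Baseline 1 halve, and one with Baseline 10 rises 1.5-fold.
- Mean change: (7 × (−0.5) + 5)/8 = +0.19
- Median change: −0.50
- Geometric mean ratio: (0.5⁷ × 1.5)^(1/8) = 0.57

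The mean points the wrong way; the planned median and the planned geometric means do not.

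**7. The zero rule.** If the zero-at-predose rule is applied to cGremlin-1, its Baseline is zero, and neither a Baseline geometric mean nor a ratio exists. The rule suits a drug concentration before the first dose, not an endogenous marker whose Baseline is that same sample.

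**The case against.** The case against has real weight, and most of it narrows the point.

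- **Scale.** The SAP never says the change is absolute, and separate table shells govern the displays. This stands. A plain difference is an inference, though the natural one, because percentage change is named separately and not invoked. If another scale was meant, the text should say so.
- **A reader might infer that the plan calls for a geometric mean of the change, which cannot exist for negative values.** The documents do not support this. The geometric statistics belong to concentration, and the default statistics for a change all exist for negative differences.
- **A reader might infer that no geometric measure of the effect can be formed.** That is too strong. With complete pairs the planned geometric means give the point estimate. Missing pairs matter least at the end-of-infusion and 4-hour samples in Part A1, taken on the same day as Baseline.
- **A reader might infer that high-Baseline participants dominate.** What is shown is extra influence on the mean and SD, which becomes domination only if the Baseline spread is large. The planned median resists a single extreme value, although it stays on the Baseline-dependent scale. A lognormal concentration does not by itself imply a proportional drug effect.
- **Importance.** The endpoint is exploratory, with no test or decision threshold. Nor is cGremlin-1 shown to be the main blood marker in the report: Part A also reports serum bone turnover markers there.

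What survives is that the plan states no relative scale for the effect and provides no paired ratio or CI for it.

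**Conclusion.** The concern holds in a limited form and is minor. Concentration is treated as lognormal, while the effect falls back, on the natural reading, to arithmetic summaries of differences. For a geoCV of 50% to 100% and a proportional effect, both assumed, the highest-Baseline participant in a cohort of 8 carries about twice to two and a half times an equal share (23%/12.5% = 1.8; 32%/12.5% = 2.6). Cohorts with the same fold change can then look different. The planned geometric means are a partial remedy: exact for the point estimate with complete pairs, off by the factors shown once participants leave, and silent on the CI. No wrong trial decision follows from this, because none depends on the summary.

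**What to change.** In section 9.2 of both SAPs:

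- State the scale of the change from Baseline now planned, and keep that summary.
- Add each participant's post-dose/Baseline ratio, summarized by timepoint and treatment group as a geometric mean ratio with geoCV and a 95% CI from paired log differences, in participants with both values.
- Apply the half-LLOQ rule to a BLQ Baseline, with a footnote wherever it is used.

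In section 4.2.1 (Part A) and section 4.3 (Part A1), limit the zero-at-predose rule to UCB6114 concentration.

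The cost is one derived variable and one extra table, with no new data. The remaining weakness is that a ratio depends on an imputed denominator where Baseline is BLQ, which the footnote makes visible.

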During the image analyses of FAP-stained slides from tumor biopsies at each timepoint, the tumor will be classified into 2 regions: the cancer (CN) tumor region and the invasive margin (IM) region using a pre-established digital automated algorithm. The IM region is usually a small proportion of the whole tumor and, per standard procedures at the analytical laboratory, will be identified first. As a result, there is a risk that some parts of the CN tumor region may be inaccurately classified as part of the IM region, particularly in cases when the tumor is small. Therefore, instead of using the results for the percentage of high, medium and low intensity FAP provided by the laboratory, a decision was made to back-calculate the areas of the CN tumor region and the IM region and add these together in order to re-calculate the percentage of high, medium and low intensity FAP in the whole tumor.

These back-calculated results and derived variables based on FAP test results at each timepoint are defined in [Table 9-1](#).

Table 9-1: FAP Derived Variables

Variable No.	FAP Derived Variable	Description and Calculation
1 ^[a]	Total Analyzed Tumor Area (um ²)	This is the total tumor area (um ²) across the CN tumor region and the IM region and will be calculated as the sum of the areas of the CN tumor region (um ²) and the IM region (um ²) where a

Variable No.	FAP Derived Variable	Description and Calculation
		
non-missing numeric test result is available for both the area of the CN tumor region and the area of the IM region. Note that, in cases where no IM region is defined, the area of the IM region will be recorded as 0 or 'NOT APPLICABLE', or may be missing. If the area of the IM region is recorded as 'NOT APPLICABLE' or is missing, then 0 will be assumed in this calculation and the total analyzed tumor area will be equal to the area of the CN tumor region.
 
This variable will be missing if both the areas of the CN tumor region and IM region are missing, or if one or both are 'NOT EVALUABLE' or 'NOT DIAGNOSTIC'.

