2	Measured Area of Weakly Stained FAP in the CN Tumor Region (um ²)	
This is the back-calculated area of weakly stained FAP in the CN tumor region (weak positive) and will be calculated by multiplying the area of the CN tumor region (um²) and the relative area of weakly stained FAP in the CN tumor region (%) where a non-missing numeric test result is available for both the area of the CN tumor region and the relative area of weakly stained FAP in the CN tumor region.
 
This variable will be set to 0 if one or both are missing, 'NOT EVALUABLE' or 'NOT DIAGNOSTIC'.

3	Measured Area of Moderately Stained FAP in the CN Tumor Region (um ²)	
This is the back-calculated area of moderately stained FAP in the CN tumor region (moderate positive) and will be calculated by multiplying the area of the CN tumor region (um²) and the relative area of moderately stained FAP in the CN tumor region (%) where a non-missing numeric test result is available for both the area of the CN tumor region and the relative area of moderately stained FAP in the CN tumor region.
 
This variable will be set to 0 if one or both are missing, 'NOT EVALUABLE' or 'NOT DIAGNOSTIC'.

4	Measured Area of Strongly Stained FAP in the CN Tumor Region (um ²)	
This is the back-calculated area of strongly stained FAP in the CN tumor region (strong positive) and will be calculated by multiplying the area of the CN tumor region (um²) and the relative area of strongly stained FAP in the CN tumor region (%) where a non-missing numeric test result is available for both the area of the CN tumor region and the relative area of strongly stained FAP in the CN tumor region.
 
This variable will be set to 0 if one or both are missing, 'NOT EVALUABLE' or 'NOT DIAGNOSTIC'.

Variable No.	FAP Derived Variable	Description and Calculation
5	Measured Area of Weakly Stained FAP in the IM Region (μm^2)	
This is the back-calculated area of weakly stained FAP in the IM region (weak FAP-positive) and will be calculated by multiplying the area of the IM region (μm^2) and the relative area of weakly stained FAP in the IM region (%) where a non-missing numeric test result is available for both the area of the IM region and the relative area of weakly stained FAP in the IM region.
 
This variable will be set to 0 if one or both are missing, 'NOT EVALUABLE' or 'NOT DIAGNOSTIC'.

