6	Measured Area of Moderately Stained FAP in the IM Region (μm^2)	
This is the back-calculated area of moderately stained FAP in the IM region (moderate FAP-positive) and will be calculated by multiplying the area of the IM region (μm^2) and the relative area of moderately stained FAP in the IM region (%) where a non-missing numeric test result is available for both the area of the IM region and the relative area of moderately stained FAP in the IM region.
 
This variable will be set to 0 if one or both are 'NOT EVALUABLE' or 'NOT DIAGNOSTIC'.

7	Measured Area of Strongly Stained FAP in the IM Region (μm^2)	
This is the back-calculated area of strongly stained FAP in the IM region (strong FAP-positive) and will be calculated by multiplying the area of the IM region (μm^2) and the relative area of strongly stained FAP in the IM region (%) where a non-missing numeric test result is available for both the area of the IM region and the relative area of strongly stained FAP in the IM region.
 
This variable will be set to 0 if one or both are missing, 'NOT EVALUABLE' or 'NOT DIAGNOSTIC'.

8 ^[a]	Total FAP-Positive Tumor Area (μm^2)	
This is the total FAP-positive area across the CN tumor region and the IM region (whole tumor) and will be calculated as the sum of component derived variables 2-7.
 
If all 6 component variables are 0 then this derived variable will be missing.

9 ^[a]	Total Measured Area of Weakly Stained FAP (μm^2)	This is the total weak FAP-positive area across the CN tumor region and the IM region (whole tumor) and will be calculated as the sum of component FAP derived variables 2 and 5.
10 ^[a]	Total Measured Area of Moderately Stained FAP (μm^2)	This is the total moderate FAP-positive area across the CN tumor region and the IM region (whole tumor) and will be

Variable No.	FAP Derived Variable	Description and Calculation
		calculated as the sum of component FAP derived variables 3 and 6.
11 ^[a]	Total Measured Area of Strongly Stained FAP (um ²)	This is the total strong FAP-positive area across the CN tumor region and the IM region (whole tumor) and will be calculated as the sum of component FAP derived variables 4 and 7.

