12 ^[a]	Total Relative Area of Weakly Stained FAP (%)	This is the percentage of weak FAP expression across the CN tumor region and IM region (whole tumor) and will be calculated using component FAP derived variables 1 and 9 as $(\text{Total Measured Area Of Weakly Stained FAP} / \text{Total Analyzed Tumor Area}) \times 100$ If the total analyzed tumor area is missing then this variable cannot be calculated and will be missing.
13 ^[a]	Total Relative Area of Moderately Stained FAP (%)	This is the percentage of moderate FAP expression across the CN tumor region and IM region (whole tumor) and will be calculated using component FAP derived variables 1 and 10 as $(\text{Total Measured Area Of Moderately Stained FAP} / \text{Total Analyzed Tumor Area}) \times 100$ If the total analyzed tumor area is missing then this variable cannot be calculated and will be missing.
14 ^[a]	Total Relative Area of Strongly Stained FAP (%)	This is the percentage of strong FAP expression across the CN tumor region and IM region (whole tumor) and will be calculated using component FAP derived variables 1 and 11 as $(\text{Total Measured Area Of Strongly Stained FAP} / \text{Total Analyzed Tumor Area}) \times 100$ If the total analyzed tumor area is missing then this variable cannot be calculated and will be missing.
15 ^[a]	Total Relative FAP-Positive Tumor Area (TPS) (%)	This is the total proportion score which is the percentage of FAP-positive area across the CN tumor region and the IM region (whole tumor) and will be calculated using component derived variables 1 and 8 as $(\text{Total FAP-Positive Tumor Area} / \text{Total Analyzed Tumor Area}) \times 100$ If the total analyzed tumor area is missing then this variable cannot be calculated and will be missing.

Variable No.	FAP Derived Variable	Description and Calculation
16 ^[a]	Total FAP Histoscore	
This is a histoscore for the combined CN tumor region and IM region (whole tumor) and will be calculated as a weighted score based on component derived variables 12, 13 and 14 as
 $(1 \times \text{Total Relative Area of Weakly Stained FAP}) + (2 \times \text{Total Relative Area of Moderately Stained FAP}) + (3 \times \text{Total Relative Area of Strongly Stained FAP})$

CN=cancer; FAP=fibroblast activation protein, IM=invasive margin, TPS=total proportion score.

^[a] Included in the listing of FAP test results.

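### The FAP derivation rules score unreadable staining as negative, and they drop a measured zero from TPS while the histoscore keeps it

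*SAP*

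**What the plan says.** Section 9.2 of each SAP defines sixteen FAP variables (Table 9-1 in Part A1, Table 9-2 in Part A).

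- **Variable 1**, total analyzed area, is the denominator and depends on region areas only: "This variable will be missing if both the areas of the CN tumor region and IM region are missing". It is also missing when either area is coded NOT EVALUABLE or NOT DIAGNOSTIC.
- **Variables 2-7** are stained areas by intensity in the cancer (CN) region and the invasive margin (IM). For 2-5 and 7: "This variable will be set to 0 if one or both are missing", and likewise for NOT EVALUABLE or NOT DIAGNOSTIC. Variable 6 leaves out the missing case: "This variable will be set to 0 if one or both are 'NOT EVALUABLE' or 'NOT DIAGNOSTIC".
- **Variable 8**, total FAP-positive area, sums variables 2-7, but "If all 6 component variables are 0 then this derived variable will be missing".
- **Variables 9-11** are plain sums by intensity. Variable 9, for example, is "calculated as the sum of component FAP derived variables 2 and 5".
- **Variables 12-14** divide 9-11 by variable 1, and **variable 15** (TPS) divides variable 8 by variable 1. Their only missing-data rule is "If the total analyzed tumor area is missing then this variable cannot be calculated and will be missing".
- **Variable 16**, the histoscore, weights variables 12-14 by 1, 2 and 3 and does not use variable 8.

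In Part A1, TPS and histoscore are summarized at each timepoint, and "changes from Baseline in TPS and total FAP histoscore at the On-Treatment timepoint will be listed and summarized by treatment group". Part A lists the results without summarizing them.

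**The concern.** A zero and an unreadable result are different facts, and these rules confuse them in two ways.

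First, a region with a numeric area but unreadable staining contributes 0 to the numerator and its full area to the denominator. It is treated as tissue shown to be FAP-negative.

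Second, the all-zero rule on variable 8 cannot tell a sample in which every reading was 0 from one in which no reading was possible. It acts on TPS alone, so the two scores can disagree for the same sample.

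Part A1 uses change from Baseline in these scores to look for a pharmacodynamic effect. A false reduction can arise from partial staining failure on treatment, and a complete loss of FAP on treatment is removed from the TPS summary. Section 9.2 of the Part A1 SAP uses the mean of the Baseline samples as the reference, so a wrong Baseline value also shifts every On-Treatment change for that participant.

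The plan avoids this elsewhere: the Gremlin-1 and pSMAD1/5/8 histoscores are missing when there are no test results, and an unevaluable Ki67 result is categorized as not done.

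**Working it through.** The plan gives no figure to reproduce, so the check applies the table rules to test samples.

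**Assumed inputs (not in the documents).** CN area 800,000 and IM area 200,000 um², so variable 1 = 1,000,000. Weak/moderate/strong staining is 20/10/5% in CN and 30/15/10% in IM. Relative areas are read as percentages, that is, divided by 100 before multiplying.

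**Formulas.** Component = region area × relative area. TPS = 100 × variable 8 / variable 1. Histoscore = 1 × weak % + 2 × moderate % + 3 × strong %, each taken over variable 1.

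**Fully read sample.**
- Weak: 160,000 + 60,000 = 220,000, or 22%
- Moderate: 80,000 + 30,000 = 110,000, or 11%
- Strong: 40,000 + 20,000 = 60,000, or 6%
- TPS = 390,000 / 1,000,000 = 39%; histoscore = 22 + 22 + 18 = 62

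**The same areas under the plan's rules:**

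| Sample | Weak / moderate / strong % | TPS | Histoscore |
|---|---|---|---|
| All readings available | 22 / 11 / 6 | 39 | 62 |
| CN weak reading unreadable | 6 / 11 / 6 | 23 | 6 + 22 + 18 = 46 |
| All IM readings unreadable | 16 / 8 / 4 | 28 | 16 + 16 + 12 = 44 |
| All CN readings unreadable | 6 / 3 / 2 | 11 | 6 + 6 + 6 = 18 |
| All readings unreadable, areas numeric | 0 / 0 / 0 | missing | 0 |
| All readings measured as 0 | 0 / 0 / 0 | missing | 0 |
| CN area NOT EVALUABLE | not calculable | missing | missing |

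Rows 2-4 differ from row 1 only in readability. If the tumor had not changed since a fully read Baseline, row 4 would give a false change of 11 − 39 = −28 in TPS and 18 − 62 = −44 in histoscore.

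Rows 5 and 6 give identical output for opposite situations. In row 5 TPS is right and the histoscore wrong; in row 6 the reverse. In row 7 both scores are correctly missing.

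**Effect on a summary.** Take five On-Treatment samples with true TPS 0, 0, 30, 40, 50 (assumed).
- True mean: (0 + 0 + 30 + 40 + 50) / 5 = 24, n=5
- Under the all-zero rule: (30 + 40 + 50) / 3 = 40, n=3

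Three values remain, which meets the minimum for summary statistics in Section 3.1 of the Part A1 SAP. With only two left, just the minimum and maximum would be shown.

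**The case against.** The strongest points on the other side are these.

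- **Complete staining failure.** A reader might infer that any On-Treatment sample that fails staining shows up as a large fall in FAP. The rules do not support that for TPS. If every reading is unreadable, variable 8 and TPS are missing, as they should be, and only the histoscore becomes a false 0. A false fall in TPS needs partial failure: a numeric area, some staining unreadable, and some positive reading elsewhere. This stands and limits the point.
- **Direction of error.** A reader might also infer that the two scores generally err in opposite directions. In a partly unreadable sample both fall together. They part only when all six components are 0.
- **Not every component.** Substitution for a missing reading is not stated for variable 6. This stands; it is a further inconsistency in the same table.
- **Legitimate zeros.** Where no IM region exists, 0 is the correct IM component. This stands, and the fix keeps it.
- **Frequency.** Nothing in the documents shows how often the laboratory reports a numeric area with unreadable staining, or how often a tumor is wholly negative. This stands, so the sizes above are illustrations.
- **Consequence.** The endpoint is exploratory, and staining artifacts and assay comments are listed beside the derived values, so a careful reader may spot a problem sample. That helps with listings but does not correct group means or changes from Baseline. Components 2-7 carry no listing flag in Table 9-1, so a substituted zero is not displayed as such among the derived variables.

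**Conclusion.** The point holds as a derivation error in an exploratory biomarker and should be corrected. Two faults follow directly from the tables. Unreadable staining within a region of known area is scored as negative, which biases TPS and histoscore downward in partly unreadable samples. The all-zero rule removes measured zeros from TPS and is not mirrored in the histoscore, so an all-zero sample always has one score wrong.

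With the assumed inputs, partial failure moves TPS from 39 to between 11 and 28 and the histoscore from 62 to between 18 and 46. Dropping two true zeros out of five moves a mean TPS from 24 to 40. Actual sizes depend on how often such samples occur, which the documents do not say.

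The reach is limited to exploratory Part A1 summaries and changes from Baseline, and to listings in Part A. Samples in which a region's area is itself coded NOT EVALUABLE or NOT DIAGNOSTIC are handled correctly.

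**What to change.** In both tables:

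1. Set a component to 0 only when the measured value is 0 or the region is absent (IM area 0, NOT APPLICABLE, or missing with no IM region defined).
2. Set it to missing when the region has an area but the reading is missing, NOT EVALUABLE or NOT DIAGNOSTIC. Use the same wording for variable 6 as for the others.
3. Carry missing through whichever of variables 8-16 depend on that component, so that TPS and histoscore follow one rule.
4. Delete the all-zero rule on variable 8, so that a measured zero gives TPS = 0.

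Under these rules, row 6 of the table gives 0 for both scores, and rows 2-5 give missing for both. The cost is an edit to each table, a small amount of reprogramming and slightly fewer evaluable samples.
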